### 2.6 Drug Exposure

Drug exposure will be measured up to the date of PD.

Cumulative dose (mg) is the sum of all study medication doses received.

Mean, SD, Median, Q1, Q3, minimum and maximum of total amount will be reported for the treated population by treatment arm.

#### Daily dose

Mean, SD, Median, Q1, Q3, minimum and maximum of daily dose amount will be reported for the treated population by treatment arm.

Planned Dose intensity (mg/ week) Planned Dose Intensity: Planned total dose per cycle divided by number of planned weeks in the cycle

## Actual Dose intensity (mg/ week)

Mean, SD, Median, Q1, Q3, minimum and maximum of actual dose intensity for the treated population by treatment arm

Actual Dose Intensity: Actual total dose per cycle divided by number of actual weeks in the cycle.

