## 2 Methods and Analyses

### 2.1 Analyses Samples

Patients were randomized to the following two treatment arms:

- Arm 1: Palbociclib 100 mg po daily.
- Arm 2: Palbociclib 125 mg po daily 3 out of 4 weeks

The study populations for this analysis will include both the intention to treat (ITT) population and the as treated population.

Analysis of pretreatment characteristics and all efficacy outcomes such as PFS and OS, will be based on the ITT population. The efficacy data set consists of all patients regardless of actual treatment.

Those who received at least one dose of protocol therapy (i.e. the as treated population) will form the basis of the safety analyses. The response analyses will include patients with measurable disease or those with non measurable disease who experience a CR. QOL analyses will include all patients who completed at least one QOL assessment (either baseline or follow-up).

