## Relative Dose Intensity (%)

Mean, SD, Median, Q1, Q3, minimum and maximum of relative dose intensity will be reported for the treated population by treatment arm.

Relative Dose Intensity: Actual total dose intensity / planned dose intensity x 100%

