## 90% or more relative dose intensity

Number and % of patients with 90% or more relative dose intensity will be reported.

Dose intensity (mg/ week), relative dose intensity (%) and number (%) of patients will 90% or more relative dose intensity for cycle 1 and 2 will also be reported.

Dose information will be reported in table 18.

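### For a cycle cut short, the dose-intensity formula gives the 3-of-4-week arm up to 133% where the continuous arm gets 100%, so the 90% count is not the same test in both arms

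*SAP*

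**What the plan says.** SAP section 2.1 gives the regimens as "Palbociclib 100 mg po daily" in Arm 1 and "Palbociclib 125 mg po daily 3 out of 4 weeks" in Arm 2.

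Section 2.6 then builds the exposure measures in steps:

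- Planned dose intensity: "Planned total dose per cycle divided by number of planned weeks in the cycle".
- Actual dose intensity: "Actual Dose Intensity: Actual total dose per cycle divided by number of actual weeks in the cycle".
- The ratio: "Relative Dose Intensity: Actual total dose intensity / planned dose intensity x 100" percent, with no upper limit.
- The threshold summary: "Number and % of patients with 90% or more relative dose intensity will be reported". Dose intensity, relative dose intensity and the threshold count are also reported for cycles 1 and 2.
- The cut-off: "Drug exposure will be measured up to the date of PD".

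The results go into Table 18, by arm, for all treated patients. Section 2.6 gives no separate rule for a cycle that ends before its planned length. It also does not say how cycle values combine into one value per patient.

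**The concern.** In Arm 2 the planned weekly figure is an average over three dosing weeks and one week off. The actual figure is an average over whatever weeks elapsed. When a cycle ends before the week off, the actual figure covers dosing weeks only and is compared with a planned figure diluted by rest. The ratio rises above 100% although no extra dose was taken. Arm 1 has no off week, so the same interruption leaves its ratio unchanged.

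Incomplete cycles are bound to occur. Exposure is cut at the date of progression, which can fall anywhere in a cycle, and every treated patient is included. The trial compares two schedules of the same drug, and Table 18 is where their relative delivery is set side by side. A measure that reads differently in the two arms for the same adherence is a poor basis for that comparison.

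**Working it through.** The SAP states no dose-intensity figure to reproduce, so the check applies its definitions directly.

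**Inputs and assumptions.** Doses and schedules are from section 2.1 and formulas from section 2.6. Three assumptions are needed: actual weeks end at the cut-off; the off week comes last in the Arm 2 cycle; and, for the two-cycle figures, Arm 1 also has a 4-week cycle.

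**Planned intensity**

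- Arm 1: 100 × 7 = 700 mg/week, whatever the cycle length.
- Arm 2: 125 × 21 / 4 = 2625 / 4 = 656.25 mg/week.

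**Full-dose cycle cut short**

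Relative dose intensity = (dose taken / weeks elapsed) / planned intensity.

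| Cycle ends on day | Arm 1 | Arm 2 |
|---|---|---|
| 7, 14 or 21 | 700/700 = 100% | 875/656.25 = 133.3% |
| 22 | 100% | 835.2/656.25 = 127.3% |
| 24 | 100% | 765.6/656.25 = 116.7% |
| 26 | 100% | 706.7/656.25 = 107.7% |
| 28 | 100% | 656.25/656.25 = 100% |

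**Doses needed to reach 90%**

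Full-strength doses needed = 0.9 × planned intensity × weeks elapsed / dose size, rounded up.

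| Cycle ends on day | Arm 1 | Arm 2 |
|---|---|---|
| 7 | 6.3, so 7 of 7 | 4.725, so 5 of 7 |
| 14 | 12.6, so 13 of 14 | 9.45, so 10 of 14 |
| 21 | 18.9, so 19 of 21 | 14.175, so 15 of 21 |

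Two patients who each took 80% of scheduled doses up to day 21 would score 80.0% in Arm 1, below the threshold, and 0.80 × 133.3 = 106.7% in Arm 2, above it.

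**Cycles 1 and 2 pooled, cycle 2 ending on day 21 (7 weeks)**

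- Arm 1: 0.9 × 700 × 7 / 100 = 44.1, so 45 of 49 doses (92%).
- Arm 2: 0.9 × 656.25 × 7 / 125 = 33.1, so 34 of 42 doses (81%).

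**Dilution over many cycles (Arm 2, full dose, last cycle cut short, total dose over total weeks)**

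- 2 cycles, last ends on day 21: 5250/7 = 750; 750/656.25 = 114.3%.
- 4 cycles, day 21: 10500/15 = 700; 700/656.25 = 106.7%.
- 10 cycles, day 21: 26250/39 = 673.1; 673.1/656.25 = 102.6%.
- 11 cycles, day 21: 28875/43 = 671.5; 671.5/656.25 = 102.3%.
- 11 cycles, day 7: 27125/41 = 661.6; 661.6/656.25 = 100.8%.

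If cycle values are averaged instead, 10 cycles give (9 × 100 + 133.3)/10 = 103.3%.

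**Two candidate repairs**

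- *Larger of planned and actual weeks as denominator.* Full-dose patients stopping on day 7, 14 or 21 score 25, 50 or 75% in Arm 1 and 33, 67 or 100% in Arm 2. Values above 100% disappear, but the difference between arms remains.
- *Dose taken over dose scheduled to the cut-off.* Full adherence scores 100% and 80% adherence scores 80% in both arms. At day 21 the threshold needs 0.9 × 21 = 18.9, so 19 of 21 in both.

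For a delayed cycle the existing formula works: a full-dose Arm 2 cycle stretched to 35 days gives 2625/5 = 525, and 525/656.25 = 80%.

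**The case against.** The strongest reply is that the SAP does not say when actual weeks end in an incomplete cycle. If the analyst counts the full 28 days, the 133% disappears. That is true, and the result is conditional on it. But with exposure measured only up to progression, ending the count at the cut-off is the natural reading, and nothing in section 2.6 directs otherwise. Counting 28 days would also bring back the arm difference shown for the first repair above.

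It is also fair that these summaries are descriptive, that no test is attached to them, and that cumulative dose, dose discontinuation with reasons (Table 19) and reasons for going off treatment (Table 23) give other views of early stopping. That limits the consequence without making the ratio comparable between arms.

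Four stronger readings are tempting and are not supported:

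- *The formula chiefly flatters patients who stopped for toxicity.* The only cut-off in section 2.6 is progression. Nothing there ends the cycle of a patient who stops for toxicity on the day of stopping.
- *Early stoppers scoring 100% in Arm 1 is itself an error.* That is ordinary on-treatment dose intensity. The distinct fault is the extra third in Arm 2.
- *Nearly a third of doses can be missed.* The algebraic limit is 32.5%, but in whole full-strength doses at day 21 it is 6 of 21 (28.6%): 14 doses give 88.9% and 15 give 95.2%.
- *Any truncated early cycle decides the flag.* Within a single cycle ending by day 21, the flag differs from an adherence-based one only for Arm 2 patients who took about 67.5% to 90% of the scheduled dose. The SAP gives no basis for estimating how many there will be.

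**Conclusion.** The point holds as a fault in a stated formula. For a cycle ending by day 21, Arm 2's relative dose intensity is overstated by a factor of 4/3 relative to adherence and Arm 1's is not; the excess fades to nothing by day 28. The 90% count is therefore easier to meet in Arm 2. This rests on actual weeks ending at the cut-off and on the off week coming last.

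The effect is concentrated in patients with few cycles and in the cycle 1 and 2 figures. For patients with ten or more cycles it is about 1 to 3 points on a total-dose-over-total-weeks basis. It does not touch the PFS hazard ratio, and the SAP does not show that any conclusion about the arms would change. It should still be corrected, because the bias runs in one direction in a trial that compares schedules.

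**What to change.** Add a rule to section 2.6 for incomplete cycles: relative dose intensity is the dose taken divided by the dose scheduled up to the cut-off date under the assigned schedule. Keep actual weeks as the denominator for completed or delayed cycles. Apply the rule to the overall figures, the cycle 1 and 2 figures and both 90% counts in Table 18. Do not substitute the larger of planned and actual weeks, which still favours Arm 2.

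The cost is a short wording change and a small re-derivation from dosing data already collected. Some Arm 2 figures will become lower.

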## Relative Dose Intensity (%)

Mean, SD, Median, Q1, Q3, minimum and maximum of relative dose intensity will be reported for the treated population by treatment arm.

Relative Dose Intensity: Actual total dose intensity / planned dose intensity x 100%

## 90% or more relative dose intensity

Number and % of patients with 90% or more relative dose intensity will be reported.

Dose intensity (mg/ week), relative dose intensity (%) and number (%) of patients will 90% or more relative dose intensity for cycle 1 and 2 will also be reported.

Dose information will be reported in table 18.

## Dose modification for palbociclib

- Any modification: Yes / No
- If yes, reason of dose modification.

Number and percentage of dose modification will be reported for treated population by treatment arm.

## Dose reduction for palbociclib

- Any reduction: Yes / No
- If yes, reason of dose reduction

Number and percentage of dose reduction for treated population by treatment arm

## Dose discontinuation for palbociclib

- Any discontinuation: Yes / No
- If yes, reason of dose discontinuation

Number and percentage of dose discontinuation will be reported for treated population by treatment arm

Number and percentage of drug modification/reduction/discontinuous will be reported for treated population by treatment arms (table 19).

## 2.7 Safety

### 2.7.1 Definitions and variables

All toxicity/side effects data collected post randomization will be included in the analyses of toxicities.

#### 2.7.1.1 Non-hematologic adverse events (CTCAE 4.0)

Non-hematologic adverse events will be summarized according to CTC AE 4.0 (table 20).

Number and % of grade 3 or 4 neutropenia, febrile neutropenia, infection and fatigue

#### 2.7.1.2 Hematology/Biochemistry (CTCAE 4.0)

Hematology/Biochemistry experienced will be reported according to CTC AE 4.0 (table 21).

Incidence of grade 3 or 4 neutropenia, anemia and thrombocytopenia by arm

Cumulative incidence curve for time to first episode of grade 3 or 4 neutrophils (in Hematology/Biochemistry from) by arm for all treated patients using the Kaplan-Meier method (cumulative incidence = 1 – KM). Patients without any grade 3 or 4 neutrophils will be censored at last time of assessment. (Figure 3).

Median time to neutrophil nadir count on study (range)

Median time to first episode of grade 3 or 4 neutropenia (range).

#### 2.7.1.3 Serious adverse event (SAE)

SAE will be listed by treatment arm (table 22). SAE that met the protocol requirements for expedited reporting (serious, unexpected and related) will be identified.

### 2.8 Off study and death

Patients off-study (off protocol treatment): Number and % of all treated patients. Reason for going off-study: Number and % of all treated patients will be presented (table 23).

Deaths within 30 days from last treatment administration will be reported. Cause of death within 30 days from last treatment administration: Number and % of all treated patients will be presented (table 24).

### 2.9 Quality of Life

#### 2.9.1 Definitions and Variables

##### 2.9.1.1. EORTC QLQ-C30

There are five functional domains and three symptom domains that can be derived from EORTC QLQ-C30 (see below for definitions). If the number of unanswered questions in each domain is within a limit specified with the definition for each domain, the score is calculated as for function domains of Physical, Emotional, Cognitive and Social:

$$\text{Score} = 100 - (((\text{Total score for the answered questions} / (\text{Total questions answered})) - 1) * 100 / 3).$$

For symptom domains:

$$\text{Score} = (((\text{Total for the answered questions} / (\text{Total questions answered})) - 1) * 100 / 3)$$

Otherwise, the score will be recorded as “missing”. For each single item, the score will be recorded as “missing” if the answer to this item is missing.

Functional Domains:

Physical:	Questions: 1, 2, 3, 4, 5, 6, 7
Score=missing if number of above questions not answered is greater than 3;	
Emotional:	Questions: 21, 22, 23, 24
Score=missing if number of above questions not answered is greater than 2;	
Cognitive:	Questions: 20, 25
Score=missing if number of above questions not answered is greater than 0;	
Social:	Questions: 26, 27
Score=missing if number of above questions not answered is greater than 0;	

Symptom Domains:

Fatigue:	Questions: 10, 12, 18
Score=missing if number of above questions not answered is greater than 1;	
Nausea and vomiting:	Questions: 14, 15
Score=missing if number of above questions not answered is greater than 0;	
Pain:	Questions: 9, 19
Score=missing if number of above questions not answered is greater than 0.	

There are also six single items in EORTC QLQ-C30 pertaining to common symptoms and one global assessment that can be derived from EORTC QLQ-C30. The single items are:

Single Items:

Dyspnea:	Question 8;
Sleep/Insomnia:	Question 11;
Appetite:	Question 13;
Constipation:	Question 16;
Diarrhea:	Question 17;
Financial:	Question 28.

They are all scored using the following formula:

$$\text{Score} = (\text{Answer to the question-1}) * 100/3.$$

The Global Assessment includes Questions 29 and 30. If number of the questions not answered is greater than 0, its score will be “missing”; Otherwise,

$$\text{Score} = ((\text{Total for the answered questions}/(\text{Total questions answered}))-1)*100/6.$$

Axillary

Axillary module (Question 31 to 33):

$$\text{Score} = 100 - (((\text{Total score for the answered questions}/(\text{Total questions answered}))-1)*100/6).$$

Score=missing if number of above questions not answered is greater than 2;

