### 2.9.2.4 QOL response analysis

QOL response is calculated as follows for a functional domain: A change score of 10 points from baseline was defined as clinically relevant. Patients will be assessed as improved if they have reported a score of 10-points or better than baseline at any time of the QOL assessment. Conversely, patients will be assessed as worsened if there is a reported score that is at least 10 points worse than baseline at any time of the QOL assessments without meeting the criteria for improved. Patients whose scores are intermediate between these values at every QOL assessment will be considered as stable. In contrast to functional domains, for the determination of patient's QOL response, classification of patients into improved and worsened categories is reversed for symptom domains and single items. A Chi-square test will be performed to compare the distributions of these three categories between two arms (improved, stable or worse).

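### The three-item axillary module is scored from a single answer, a looser missing-item limit than for any other multi-item quality-of-life scale in the SAP

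*SAP*

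**What the plan says.** Section 2.9.1.1 fixes the scoring of each quality-of-life scale. It opens with a conditional rule, "If the number of unanswered questions in each domain is within a limit specified with the definition for each domain", so each scale carries its own limit on unanswered items.

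The limits are:

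- Physical (7 items): "Score=missing if number of above questions not answered is greater than 3".
- Emotional (4 items): the limit is 2 unanswered.
- Fatigue (3 items): "Score=missing if number of above questions not answered is greater than 1".
- Cognitive, Social, Nausea and vomiting, and Pain (2 items each): "Score=missing if number of above questions not answered is greater than 0". The Global Assessment (2 items) has the same limit.
- "Axillary module (Question 31 to 33"), three items: "Score=missing if number of above questions not answered is greater than 2".

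The axillary score is 100 minus a rescaled mean, and the rescaling ends in "answered}))-1)*100/6". The same multiplier of 100/6 is used for the Global Assessment (Q29-30), without the subtraction from 100. Questions 1 to 28 use 100/3.

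Section 2.9.2.4 takes a change of 10 points from baseline as clinically relevant. It defines improved and worsened for functional domains and then states that "classification of patients into improved and worsened categories is reversed for symptom domains and single items". Section 2.9.2 makes all quality-of-life analyses exploratory.

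**The concern.** A limit of two unanswered items out of three excludes only a module left entirely blank. Any patient who answers one of the three questions gets a score, and that score enters the analysis with the same standing as a complete one. The same limit of 2 is used for the Emotional domain, but that domain has four items, so there it still secures half of them.

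The consequence is noise in the change scores. A patient may answer all three questions at one visit and one at another. The two scores then rest on different items, and the difference between them can come from which item was answered, not from any change in the patient. The 10-point rule of section 2.9.2.4 looks for a change of that size at any assessment, so one sparse form can decide a patient's category. The same scores would also feed the Wilcoxon comparisons and the mixed model of section 2.9.2.3.

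**Working it through.** There is no stated figure to reproduce; the check is arithmetic on the scoring rules.

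**Step 1. Minimum number of answers.** Items and limits come from section 2.9.1.1. Minimum answered = items − unanswered items allowed.

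| Scale | Items | Unanswered allowed | Minimum answered | Share |
|---|---|---|---|---|
| Physical | 7 | 3 | 4 | 57.1% |
| Emotional | 4 | 2 | 2 | 50.0% |
| Fatigue | 3 | 1 | 2 | 66.7% |
| Cognitive, Social, Nausea and vomiting, Pain, Global | 2 | 0 | 2 | 100% |
| Axillary | 3 | 2 | 1 | 33.3% |

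The axillary module is the only scale below one half. The direct comparison is with Fatigue, which has the same number of items.

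**Step 2. Effect of one category on one item.** The printed formula is score = 100 − (mean − 1) × 100/6. With k items answered, a shift of one category on one item changes the mean by 1/k and the score by 100/(6k):

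- k = 3: 100/18 = 5.6 points
- k = 2: 100/12 = 8.3 points
- k = 1: 100/6 = 16.7 points

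Only with one answered item does a single category pass the 10-point threshold.

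**Step 3. Same patient, different items answered.** Suppose the underlying answers stay at 1, 1 and 4. Such answers are possible with four or with seven categories.

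- All three answered: mean 2; 100 − 1 × 100/6 = 83.3.
- Only one of the items at 1 answered: 100 − 0 = 100, an apparent change of +16.7.
- Only the item at 4 answered: 100 − 3 × 100/6 = 50, an apparent change of −33.3.

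Both exceed 10 points, although nothing has changed.

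**Step 4. The same patient under a two-item minimum.**

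- Answers 1 and 1: mean 1; score 100, an apparent change of +16.7.
- Answers 1 and 4: mean 2.5; 100 − 1.5 × 100/6 = 75, an apparent change of −8.3.

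The tighter limit does not remove such shifts, but in this example it halves the largest one, from 33.3 to 16.7.

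**Step 5. What the divisor implies.** The SAP does not give the answer categories of Q31-33, so both plausible codings are shown.

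- Coded 1 to 7: lowest score 100 − 6 × 100/6 = 0, so the range is 0 to 100, as intended.
- Coded 1 to 4: lowest score 100 − 3 × 100/6 = 50, so the range is only 50 to 100. With 100/3 it would be 0 to 100.

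**The case against.** The best defence of the limit is that section 2.9.1.1 lets each domain have its own and states no general rule that half the items must be answered. That is correct: the axillary limit departs from a pattern that all the other scales follow, and contradicts no written rule. It is also true that only forms with exactly two of the three items blank are affected. The SAP gives no frequency for these, and they are likely to be few. Both arguments bear on how serious the point is. Neither explains why a three-item module should need fewer answers than three-item Fatigue.

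Two stronger readings are tempting and are not supported.

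- **That the divisor of 6 is wrong, so that changes appear at half their true size.** This needs four answer categories for Q31-33, which the SAP does not state. Those questions follow directly on Q29-30, which are also scored with 100/6. If they have seven categories, the formula is right.
- **That improved and worsened are swapped as the plan is written.** Section 2.9.2.4 reverses direction only for symptom domains and single items, and section 2.9.1.1 lists the axillary module under neither. Its subtraction from 100 is the functional form and fits the default that higher is better. Labels would swap only if an analyst chose to treat the module as a symptom scale, which the SAP does not tell anyone to do. Even then, not every classified patient would change: improved takes precedence, so a patient who crosses 10 points both ways is improved under either direction.

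What remains on direction is a wording gap: section 2.9.2.4 names neither the axillary module nor the Global Assessment.

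**Conclusion.** The point holds for the missing-item limit and is minor. One answer of three (33.3%) produces an axillary score, against at least 50% for every other multi-item scale and 66.7% for the other three-item scale, with no reason given. On a one-item form, one category is worth 16.7 points in place of 5.6, which is enough on its own to pass the 10-point threshold. These figures rest on the formula as printed and need no assumption about the number of answer categories, beyond the example's use of a category 4.

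The effect is confined to forms with two of three items blank, in analyses the SAP calls exploratory. The PFS hazard ratio, which is the primary objective, is untouched. The divisor and the direction of the score are matters to confirm, not demonstrated errors.

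**What to change.** In section 2.9.1.1, set the axillary score missing if more than one of Q31-33 is unanswered, matching Fatigue. This is one line of SAP text and one line of scoring code. The cost is the loss of the few scores that rest on a single item.

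At the same time, confirm two things:

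- Check the divisor against the printed questionnaire. It stays at 6 if Q31-33 are coded 1 to 7; if they are coded 1 to 4, it should be 3.
- Add a sentence to section 2.9.2.4 saying that a higher score is better for the axillary module and for the Global Assessment. For the axillary module, first check that higher answers to Q31-33 mean a worse state, as the subtraction from 100 implies.

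Neither confirmation costs any data.
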